5. TREATMENT OF SUBJECTS

5.1 Investigational product/treatment

The standard of care for the patients eligible for the TORPEDO-NL trial is parenteral anticoagulation and systemic thrombolysis (Actilyse® [manufactured by Boehringer Ingelheim Pharmaceuticals, Inc., Ingelheim am Rhein, Germany] 10mg bolus followed by 90mg in two hours). The intervention consists of parenteral anticoagulation and immediate CDT (FlowTriever or Indigo) without systemic or locally administered systemic thrombolysis. Thrombectomy is performed according to the IFU for the particular device and occurs via echoguided femoral or jugular venous access by an interventional cardiologist, interventional radiologist or vascular surgeon. The catheter is advanced over a preplaced guidewire across the right heart into the pulmonary arteries to the location of proximal thrombus. After removal

of the dilator, the thrombus is extracted by controlled volume aspiration through an aspiration catheter using either a syringe or the dedicated aspiration system depending on the device of choise, with multiple aspirations performed as needed. Investigators will determine when to terminate the procedure based on their assessment patients respiratory and hemodynamic status. Procedural objectives will be clearly stated prior to the intervention and respiratory and hemodynamic parameters, including pulmonary artery pressures, will be evaluated pre- and post-thrombectomy per protocol to inform each operator's decision to determine completion. Revaluation of the patient's condition should be carried out using blood loss as a reference, establishing 400 cc of blood loss as a cut-off value. The type and dosage of anticoagulant prescribed to each patient at discharge will be determined by local practice but administration will initially be parenteral for at least 24h after randomization. Participating centres have an institutionalized multidisciplinary Pulmonary Embolism Response Team (PERT) or EXPERT-PE team in place. The intervention team should have ample experience with endovascular interventions. At least one member of the intervention team should have sufficient experience with thrombectomy for PE and should have completed at least 3 full procedures (logged) with one of the devices. Procedures that have been carried out by two team members (for example, in a training setting) do count.

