8.3 Study procedures

The study starts as soon as the patients is identified as eligible for inclusion and randomised. All patients, i.e. both study arms, will be treated with an UFH bolus after diagnosis. Patients randomised to the usual care arm will be treated with UFH or LMWH with systemic thrombolysis. Patient randomised to the intervention will be treated with UFH or LMWH (see paragraph 5.2 for specifics) and transferred to the cath lab and subjected to the thrombectomy. All further diagnostic tests (e.g. echocardiography, repeated blood test) are used along clinically relevant but not dictated by this protocol. No biomarkers or imaging test at baseline or follow-up will be required for the study. The SCAI SHOCK stage will be assessed at baseline and every 6 hours starting from randomization until the patient is stabilized and transferable to a normal ward (**Table 1**).^{26,27} At 48 hours following randomisation, the amount of oxygen supplementation (I O_2 /min) is noted in the medical chart. Patients will be contacted by the Sponsor on day 7 (± 2 days), at 3 months (± 1 week), at 6 months (± 1 week), at 9 months (± 1 week) and at 12 months (± 2 weeks) by e-mail to complete the PROMS questionnaire(s) (**Table 2**).

Stage	Α	В	С	D	E
Condition	Hemodynamically	Hemodynamically	Hypoperfusion	Failure to	Extremis /
	stable	unstable	= Shock	stabilize with	refractory shock
				initial therapy	
Hypotension:					
- SBP	>90 mm Hg	60-90 mm Hg	60-90 mm Hg	60-90 mm Hg	<60 mm Hg
- MAP	>65 mm Hg	50-65 mm Hg	50-65 mm Hg	50-65 mm Hg	<50 mm Hg
		OR	AND	AND	OR
Hypoperfusion					
- Arterial lac-					
tate	<2 mmol/L	2-5 mmol/L OR	2-5 mmol/L O R	>5-10 mmol/L	>10 mmol/L
			200-500 U/L	OR	OR
- ALAT	<200 U/L	200-500 U/L	≥ 7.2	>500 U/L	< 7.2
- рН	≥ 7.2	≥ 7.2		≥7.2	
		AND	AND	OR	OR
Treatment	No Drugs	No Drugs	No Drugs	2 Drugs	≥3 Drugs OR
intensity	No Devices	No Devices	No Devices		Device
			OR	OR	OR
			1 Drug without	1 Drug with	Out-of- or in-
			hypotension or	persistent	hospital cardiac
			hypoperfusion	hypotension or	arrest
				hypoperfusion	

Table 1: SCAI SHOCK stage overview. SBP = systolic blood pressure; MAP = mean arterial pressure; ALAT = alanine aminotransferase, Drugs = intravenous vaso-active drugs, Devices = RV support or VA-ECMO; hypotension = SBP ≤90 mm Hg or MAP ≤65 mm Hg

	7 Days	3 Months	6 Months	9 Months	1 Year
EQ-5D-5L	Х	Х	Х	Х	Х
ICHOM-VTE -	Х	Х	Х	Х	Х

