10.2 Secondary study parameter(s)

For continuous secondary endpoints (e.g., DOOR in the first 7 days after randomization), we will estimate mean or median difference between trial arms using an Independent Samples t

Test (mean difference) or a Mann Whitney-U test (median difference), depending on the normality of the distribution. Regarding categorical secondary outcomes, differences between the trial arms will be analyzed using a Chi-square test or Fisher's exact test, when appropriate. Repeated measures secondary outcomes are analyzed using mixed-effects (longitudinal) regression models. Outcomes will be (numerically) stratified according to the type of thrombectomy (FlowTriever vs. Indigo). A per-protocol analysis is performed as a sensitivity analysis. Both R studio and Graphpad software will be used for statistical analysis and making graphs, respectively. A two-sided p-value <0.05 is considered statistically significant. Missing data, where applicable, will be imputed with the use of multiple imputation under the missing-at-random assumption with chained equations. Outcome variables will not be imputed, as is the convention in randomized controlled trials. Patient safety will be monitored by a Data Safety Monitoring Board (DSMB) that will include several senior researchers. Subgroup analyses will be performed (if feasible, i.e. if numbers per subgroup are sufficiently large) for man versus women, age below 75 or 75 and older, different devices used and subtype of high-risk PE.

A cost effectiveness analysis (CEA) will be performed after a time horizon of one year for the primary outcome and QALYs. QALYs will be estimated using the EQ-5D-5L administered at day 7 and after 3, 6, 9 and 12 months, the Dutch tariff, and the "Area under the Curve" approach.^{28,29}

The economic evaluation will be performed in accordance with the 'Dutch Guideline for economic Evaluations'.¹⁸ In the main analysis, the societal perspective will be applied, meaning that all costs will be included irrespective of who pays or benefits (i.e. the cost of the intervention, other healthcare use, informal care, as well as productivity losses from unpaid and paid work). Intervention costs will be micro-costed, all other costs will be measured using cost questionnaires administered at 7 and after 3, 6, 9 and 12 months, and valued using standard prices provided by the 'Dutch Manual for Costing Studies in Health Care'.³⁰

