Cost and effect differences will be estimated, while appropriately accounting for the skewed nature of costs (bootstrapping), correlated costs and effects (bivariate regression model), missing data (multiple imputation), baseline imbalances (baseline adjustment), and the clustered nature of data (mixed model), if applicable.(38) Then, incremental cost-effectiveness ratios (ICER) will be calculated by dividing the difference in costs by the difference in effects. The uncertainty stratified around the ICER and will be estimated using bias-corrected and accelerated bootstrapping with 5.000 replications and graphically presented on cost-effectiveness planes. These planes will indicate the probability that an intervention is cost-effective compared to usual care at different values of willingness to pay (cost-effectiveness acceptability curve).²⁹ To assess the robustness of the results, various sensitivity analyses will Version 2.1: 16-12-2024 30 of 38

be performed (e.g. healthcare perspective, complete-case analysis, per-protocol analysis, human capital approach versus friction cost approach).²⁹

A budget impact analysis (BIA) will be conducted according to ZonMw's 'BIA, leidraad en rekentool' and ISPOR's principles of good practice.³¹ The budget impact analysis will be based on the Dutch population, and hence Dutch incidence data will be used. Perspectives that will be considered are the societal, government (Budget Kader Zorg), and insurer perspective. The cost of the intervention mix will be valued using Dutch standard costs for the societal perspective, actual NZA tariffs for the government perspective, and average tariffs NZA for the insurer perspective. Different scenarios will be evaluated including the following: 1) the intervention is not implemented, i.e. all patients will receive usual care, 2) the intervention is offered to the whole patient population. These subgroups will be defined based on the results of the study, e.g. subgroups who particularly benefitted from the intervention (e.g., type of thrombectomy, sex, presence of cancer). Uncertainty will be estimated using probabilistic sensitivity analyses.

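### The subgroup by device used is not defined for control patients, and type of thrombectomy is given as an example of a benefit subgroup for the budget impact analysis

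*Protocol*

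**What the plan says.** The subgroup list is in section 10.2 of the protocol. Besides sex and age it names "different devices used and subtype of high-risk PE". The only condition attached is size: "if feasible, i.e. if numbers per subgroup are sufficiently large". The same section separately announces a split by device: "Outcomes will be (numerically) stratified according to the type of thrombectomy (FlowTriever vs. Indigo".

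The arms differ in whether a device exists at all. In section 5.1, "The intervention consists of parenteral anticoagulation and immediate CDT (FlowTriever or Indigo" describes the CDT arm, and the aspiration method is said to vary "depending on the device of choise". In section 8.3, "Patients randomised to the usual care arm will be treated with UFH or LMWH with systemic thrombolysis". Section 8.2 stratifies randomisation by centre only. Nothing in the protocol asks for an intended device to be recorded before allocation.

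The budget impact paragraph of section 10.2 says "These subgroups will be defined based on the results of the study", and illustrates this with "subgroups who particularly benefitted from the intervention (e.g., type of thrombectomy, sex, presence of cancer".

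**The concern.** Sex, age and type of high-risk PE are baseline features present in both arms, so each level contains randomised CDT and control patients. Device used is different in kind: it is settled after allocation and only for patients who undergo CDT. Placing it in the same list invites a treatment effect per device for which no controls are identified, and the size condition cannot supply them.

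There is also a tension with the intention-to-treat rule in section 10, which analyses patients as assigned whatever treatment was actually delivered. Section 8.6 foresees patients whose allocated reperfusion is not given. A CDT patient who dies or deteriorates before the procedure has no device used and would fall out of both device groups, taking an early event along.

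At stake is the reading of a secondary result. A chance or case-mix difference between two commercial systems could be reported as a subgroup finding of a randomised trial and then enter a payer-facing scenario as device-specific benefit.

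**Working it through.** **Inputs.** Section 4.4 gives event risks of 0.19 (CDT) and 0.46 (systemic thrombolysis; the stated 27.5-point difference implies 0.465), a treatment OR of 3.71, 35 + 70 evaluable patients, and 37 + 74 = 111 recruited. The protocol gives no device split and no centre-specific risks, so those below are assumptions.

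**The plan's own size.** The plan gives no figure for the device question. Its sample size reproduces adequately: a two-sided 5% test with 35 and 70 patients has exact Fisher power of 79.1% at a control risk of 0.46 and 80.5% at 0.465. Drop-out: 35/0.95 = 36.8, so 37; 70/0.95 = 73.7, so 74.

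**Which comparisons are available for a device effect?**

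| Comparison | Randomised? |
|---|---|
| CDT versus thrombolysis within device used | Not defined: controls have no device |
| FlowTriever versus Indigo within CDT | No |
| Each device versus all controls | No: one side is selected by device |
| CDT versus thrombolysis within the device named before allocation | Yes, but that variable is not collected |

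**Imprecision of device versus device within CDT.** Half-width = 1.96 × √[p(1 − p)(1/a + 1/b)].
- Even split of 74 (37 and 37), p = 0.19: 1.96 × √(2 × 0.1539/37) = 1.96 × 0.091 = 0.18.
- Even split of the 70 evaluable (35 and 35): 0.18. Split 49 and 21 (70:30): 0.20.

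**Bias from a shared control group, illustrated.** Assume that device follows centre, that the two sets of centres are equal in size, that both devices have the same true OR of 3.71, and that control risk is 36% in one set and 56% in the other (46% overall). CDT risk follows from CDT odds = control odds/3.71.
- Set A: 0.5625/3.71 = 0.152, risk 13.2%.
- Set B: 1.273/3.71 = 0.343, risk 25.5%.
- Against all controls (odds 0.852): ORs 0.852/0.152 = 5.6 and 0.852/0.343 = 2.5; risk differences 32.8 and 20.5 points.
- Against own-centre controls: OR 3.71 in both; risk differences 22.8 and 30.5 points.

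Two devices with the same OR appear to differ by a factor of more than two, and the order of the risk differences reverses. With control risks of 41% and 51% the apparent ORs are 4.5 and 3.0. With equal control risks the distortion vanishes.

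**Precision of the repaired subgroup.** With an even split by device named beforehand, each level has about 37 CDT and 18.5 control patients. The variance of a risk difference is 0.46 × 0.54/18.5 + 0.19 × 0.81/37 = 0.0134 + 0.0042 = 0.0176. For the difference between the two risk differences, the half-width is 1.96 × √(2 × 0.0176) = 0.37. The repair makes the comparison valid but leaves it very imprecise.

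**The case against.** The protocol does not say how the device analysis will be done. Comparing each device with all controls is one possible reading, and section 10 leaves the detailed methods to a statistical analysis plan that is not shown here. The numerical stratification by device is legitimate description and may be all that is intended. In the budget impact paragraph, type of thrombectomy is an example within an example, the sentence refers back to subgroups not previously mentioned, and separating devices by cost is a proper use.

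Most of this stands. What remains is that section 10.2 lists device among the subgroup analyses in addition to the descriptive split. A later analysis plan can choose a comparator, but it cannot recover an intended device for control patients if device varies within a centre.

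A reader might also infer that a device subgroup is impossible in principle because each centre chooses its device. The protocol does not support this. It does not say who chooses; section 5.1 requires only that a team member has experience with one of the devices. If each centre did use a single device, centre would fix it before allocation, and controls from the same centres would be proper randomised controls. If device instead varies by patient or operator, confounding with centre is possible but not established.

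**Conclusion.** The point holds in a limited form. The subgroup by device used is undefined for controls as written, and the alternatives that use device received are non-randomised. The protocol gives such a variable as an example of a subgroup to be singled out for benefit; it does not commit to using it, so a reading that device-specific benefit will necessarily drive the budget impact analysis goes too far.

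No size can be put on the bias from the document. The figure of about 18 points is sampling error under an assumed even split, and the ORs of 5.6 and 2.5 come from assumed centre risks; neither should be read as the expected error. The matter touches one subgroup analysis and one secondary economic analysis. The primary comparison and the sample size are untouched. It is a minor point, worth acting on because the missing variable can be collected cleanly only before allocation.

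**What to change.** 1. Add one field to the web randomisation form, completed before allocation for every patient still to be randomised: the device that would be used if CDT were allocated. This should be feasible, since section 8.2 requires verification that CDT can start within 60 minutes, and section 13.2 makes device availability and catheter stock a condition of enrolment. For any patients already enrolled, use the centre's device where the centre has only one.
2. In section 10.2, define the device subgroup on that field, with a treatment-by-device interaction, labelled exploratory.
3. Keep results by device actually used as the descriptive stratification already planned.
4. In the budget impact paragraph, remove type of thrombectomy as an example of a benefit subgroup, or label it non-randomised and exploratory. Separating devices by cost can stay.

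The cost is one extra entry during an emergency randomisation and a few sentences of text. Patients already enrolled at centres that use both devices could not be classified, and the subgroup would remain too imprecise to support a claim about either device.

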1. INTRODUCTION AND RATIONALE

Patients with acute pulmonary embolism (PE) usually have good outcomes.¹ However, their prognosis may vary dramatically according to whether the patient is hemodynamically stable. High-risk PE (5-7% of hospitalized patients with PE) is defined by hemodynamic instability and encompasses the clinical presentations of cardiac arrest, obstructive shock, or persistent hypotension.² These high risk patients have 30-day mortality rates ranging from 15% to as high as 77%. However, PE patients with respiratory failure that do not fulfill shock criteria, therefore currently not considered as high risk in the ESC guideline, also show a >30% risk of death and further respiratory failure.³⁻⁶ High-risk PE patients require immediate reperfusion therapy on top of anticoagulation. The standard reperfusion treatment in these patients is thrombolytic therapy (class 1-B, 2019 European Society of Cardiology (ESC) guidelines), administered at last in part at the Intensive Care Unit (ICU), with the idea of accelerated fragmentation of the thrombus by lytic medication given systemically.² This carries a significant risk of major bleeding (10-25%) and intracranial hemorrhage (ICH, 3%).² This risk has been shown to be a major barrier for administering lifesaving systemic thrombolysis in daily practice conditions, which has been suggested to contribute to the high mortality of these patients.⁷ The need to minimize the risk of serious bleeding or to offer alternatives to systemic thrombolysis in patients with a high bleeding risk has driven the development of alternative strategies for pulmonary reperfusion. Catheter-directed therapy (CDT), which includes catheter thrombectomy ("thrombectomy") may be associated with lower morbidity and mortality as it offers patients a fast and relatively safe relief of thrombus load and associated signs and symptoms, and may thus represent a better and safer option than systemic thrombolysis.

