Core set –					
Individual					
Questions					
(Satisfaction					
with treatment					
/ Changes in					
life view)					
PEMB-QoL 40	Х	Х	Х	Х	Х
items					
PROMIS GH	Х	Х	Х	Х	Х
ten items					
PROMIS	Х	Х	Х	Х	Х
Numeric Rating					
Scale v1.0 -					
Pain Intensity					
1a_DUT_FLE					
PROMIS SF	Х	Х	Х	Х	Х
v1.0 - Dyspnea					
Severity short					
form 10a					
PVFS scale one	Х	Х	Х	Х	Х
item					

Table 2: Questionnaire overview. The y-axis represents the type of questionnaire, while the x-axis indicates the time points at which the patient receives the questionnaires.

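### Costs other than the intervention, including ICU and hospital care, are to come only from questionnaires, so cost data will be missing in step with death and acute severity

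*Protocol*

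**What the plan says.** The economic evaluation in protocol section 10.2 counts costs whoever pays. Its scope is "the cost of the intervention, other healthcare use, informal care, as well as productivity losses from unpaid and paid work". Two sources are then named, and together they cover everything: the intervention is micro-costed, and "all other costs will be measured using cost questionnaires administered at 7 and after 3, 6, 9 and 12 months". Because ICU stay, ventilation and ward days are healthcare use outside the intervention, they fall under the second source.

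Section 8.3 contacts patients on day 7 and at 3, 6, 9 and 12 months, "by e-mail to complete the PROMS questionnaire(s"). The caption of Table 2 reads: "The y-axis represents the type of questionnaire, while the x-axis indicates the time points at which the patient receives the questionnaires". The table lists seven instruments: EQ-5D-5L, the ICHOM-VTE questions, PEMB-QoL, PROMIS global health, PROMIS pain, PROMIS dyspnoea and PVFS. It has no cost questionnaire.

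For gaps, the economic paragraphs of 10.2 provide for "missing data (multiple imputation"). Earlier in 10.2, multiple imputation is specified under a missing-at-random assumption, and outcome variables are said not to be imputed.

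**The concern.** A questionnaire first given on day 7 suits stable patients. These patients are in shock, post-arrest or in respiratory failure, and the introduction reports: "These high risk patients have 30-day mortality rates ranging from 15% to as high as 77" per cent. Someone who dies before day 7 returns nothing. Someone who dies later returns nothing for the last period. A survivor still ventilated on day 7 is unlikely to answer.

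Whether a cost record exists therefore depends on death and on how severe the acute phase was. The trial expects both to be affected by treatment: section 4.4 assumes a 5-point mortality difference, and a shorter ICU and hospital stay is a stated hypothesis. The acute inpatient cost, which CDT is expected to lower, is the part measured least well, and the loss may differ by arm.

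Imputation under missing-at-random does not repair this well. A patient with no questionnaire can only be given values modelled on those who answered, and they are survivors of at least that period. The direction of the resulting bias cannot be read from the protocol, since an early death may be cheap or expensive.

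**Working it through.** **1. The plan's own figure.** No figure is given for the economic evaluation, so the arm sizes are the starting point. Section 4.4 needs 35 and 70 patients before drop-out: 35 / 0.95 = 36.8, so 37 (thrombolysis), and 70 / 0.95 = 73.7, so 74 (CDT), total 111. This reproduces and is not in dispute.

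**2. Sources set side by side.**

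| Item | Collected whether or not the patient can answer? | Named as a cost source in 10.2? |
|---|---|---|
| ICU and hospital stay to day 30 (8.1.2) | Yes, trial outcome | No |
| Organ-support days for the day-7 DOOR (8.1.2) | Yes | No |
| SCAI stage and treatment failure, 6-hourly (8.1.1, 8.3) | Yes | No |
| Cost questionnaire, day 7 to month 12 (10.2) | No | Yes, for all non-intervention costs |

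The first three cover much of the acute inpatient care. Outcomes go into Castor (12.1), and patients are followed for outcomes even when the allocated treatment is not given (8.6). Nothing in the protocol links these data to costing.

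**3. Scale.** Inputs:
- arm sizes 37 and 74 (section 4.4);
- mortality 5 points lower with CDT (section 4.4);
- lowest background 30-day mortality 15% (section 1);
- mortality 1.9% in the prospective FlowTriever study of high-risk PE (section 1), observed to discharge or 45 days, so only an approximate 30-day rate.

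Assumption: the chosen rate applies to this trial, and control exceeds CDT by 5 points.

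Expected deaths = 37 × control mortality + 74 × CDT mortality.

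- CDT 1.9%, control 6.9%: 37 × 0.069 + 74 × 0.019 = 2.6 + 1.4 = 4.0, about 4 of 111 (4%).
- Control 15%, CDT 10%: 37 × 0.15 + 74 × 0.10 = 5.6 + 7.4 = 13.0, about 13 of 111 (12%).
- Control 20%, CDT 15% (illustrative base rates): 7.4 + 11.1 = 18.5 of 111 (17%).

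**4. Ceiling within the plan's own assumptions.** Death is part of the primary composite, which is assumed to be 0.19 with CDT. CDT mortality therefore cannot exceed 19%, nor control mortality 24% if the difference is 5 points: 37 × 0.24 + 74 × 0.19 = 8.9 + 14.1 = 22.9, about 23 of 111 (21%).

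**5. What these counts are.** They are total deaths, not patients without acute-phase costs. A patient who dies after day 7 may have returned that questionnaire, while a survivor too ill to answer is not counted. The protocol gives neither number.

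**The case against.** The strongest reply is that the key data exist. Length of stay, organ support and 6-hourly status are recorded for other endpoints and could be priced. That is correct. A reader might infer that the ICU and hospital costs of the sickest patients are lost, and the protocol does not support that. What stands is that 10.2 names a different source for those costs and does not use these data.

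Four other stronger readings also go too far.

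- *Patients who died will be imputed as survivors.* No rule says so. Section 10.2 provides for imputation of missing data where applicable and never classes the time after death as missing. Handling of death may be left to the analysis plan. The risk arises because the stated source yields nothing for these patients; a later plan cannot recover questionnaires never completed, though it can use the recorded stay.
- *The cost questionnaire is e-mailed to the patient and has no schedule.* The e-mail sentence in 8.3 concerns the PROMs, and 12.1 mentions telephone as well as e-mail. Completion by the patient is the natural reading, since no proxy is named, but it is inferred. Section 10.2 does give time points, so the gap in Table 2 is an inconsistency only.
- *Deaths after day 90 will pass as non-response.* Mortality is an endpoint only to day 90, but follow-up lasts one year (section 3) and SAEs are to be reported to end of study (9.4). Section 9.2.2 limits site reporting to related SAEs, so capture is likely but not assured. Relatives of patients who die before consent are offered an appointment as well as a letter (11.2), though no cost data are sought.
- *Close to half the trial could be affected.* Control mortality of 46% is a 90-day figure from an older registry. With CDT 5 points lower, at 41%, it contradicts the assumed composite of 0.19 with CDT and would use up the whole control composite of 0.46.

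**Conclusion.** The point holds in limited form. As written, section 10.2 assigns inpatient and ICU costs to an instrument that patients who die or are gravely ill cannot complete. The resulting gaps follow outcomes that the trial expects to differ by arm, and missing-at-random imputation is a weak answer to them. The cost difference could be biased, in a direction the documents do not settle.

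Total deaths, as a rough guide to scale, are about 4 of 111 at the registry rate and about 13 of 111 at 15% control mortality, and more if mortality is higher. These counts rest on the 5-point difference and on outside mortality rates applying here. The share dying before day 7, and the share of survivors unable to answer, are unknown.

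Only the secondary cost-effectiveness objective is affected. The primary endpoint, its analysis and the sample size are untouched.

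**What to change.** In section 10.2:
- take inpatient and ICU resource use for every randomised patient, including those who die, from the eCRF and hospital records, and value it at the Dutch standard prices already named;
- keep the questionnaires for out-of-hospital care, informal care and productivity;
- set costs and utility to zero from the date of death and do not impute them, which requires that dates of death be recorded to month 12;
- if lost production after death is to be counted under the human-capital or friction-cost approach, state it as a separate calculated item;
- say how the rule against imputing outcomes sits with the imputation planned for the economic evaluation.

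In section 8.3, add the cost questionnaire to Table 2 at the time points given in 10.2, and state who completes it.

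The cost is a few sentences and one table row. Stay to day 30, organ support for the day-7 ranking and treatment-failure data are collected anyway; organ support after day 7 may need an extra eCRF field. Inpatient use after day 30 needs a chart check or stays questionnaire-based, which is a small drawback.

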To assess statistical power, the probability of the primary outcome was assumed to be 0.19 in the thrombectomy arm (based on the most recent data available) and 0.46 in the systemic thrombolysis arm (corresponding with a treatment OR of 3.71 and a risk difference of 27.5%; number needed to treat 3.6). The minimum clinically important difference was set at 27.5% based on discussion within the project group, scientific societies and patient representatives, and on clinical relevance for the difference facets of the composite endpoints. The assumed ARR of 27.5% consists of 5% decrease in mortality, 21.5% reduction in treatment failure or major bleeding and 1% reduction in ischemic stroke (the latter both based on expert opinion).¹⁸ Given a power of 80%, a two-sided α -level of 5%, and a 1:2 (systemic thrombolysis:CDT) patient allocation, 35 patients are needed in the systemic thrombolysis and 70 patients in the CDT arm. Assuming 5% drop-out, 37 patients (systemic thrombolysis) and 74 patients (CDT; total 111 patients) will be recruited. The calculation was done using G*Power (version 3.1.9.6) and is based on proportion difference tested with an anticipated OR.

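### Budget-impact subgroups are to be chosen after the results by observed benefit, with no closed list or criterion; a scenario using the chosen subgroup's own estimate would overstate benefit

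*Protocol*

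**What the plan says.** Protocol section 2 lists budget impact among the secondary objectives. Section 10.2 plans it from societal, government and insurer perspectives and numbers two scenarios: no implementation, and the intervention offered to all patients. The next sentence reads "These subgroups will be defined based on the results of the study, e.g. subgroups who particularly benefitted from the intervention", with type of thrombectomy, sex and presence of cancer as examples. Uncertainty is to be handled by probabilistic sensitivity analysis.

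Earlier in section 10.2 stands a separate list of clinical subgroups: "Subgroup analyses will be performed (if feasible, i.e. if numbers per subgroup are sufficiently large) for man versus women", followed by age split at 75, device and subtype of high-risk PE. Cancer is not on that list.

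The trial is small. Section 4.4 states that "37 patients (systemic thrombolysis) and 74 patients (CDT; total 111 patients) will be recruited".

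**The concern.** The sentence sets a selection rule: look at the results, then form subgroups from those who appeared to gain most. Four features make it weak.

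- The candidate list is open-ended and does not match the clinical subgroup list.
- It sets no threshold, interaction test or correction for selection, and does not say on which outcome benefit is judged.
- The condition on adequate numbers, attached to the clinical subgroups, is not repeated for the budget impact analysis.
- The sentence opens by pointing back to subgroups, but no subgroup scenario has been stated.

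A subgroup picked because its estimate is high has, on average, an estimate that is too high. If that estimate then feeds a budget scenario, the scenario overstates what treating that group would achieve. A sensitivity analysis whose draws centre on the selected estimate would carry the same bias.

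**Working it through.** **Inputs from Protocol section 4.4.** "the probability of the primary outcome was assumed to be 0.19 in the thrombectomy arm", and "0.46 in the systemic thrombolysis arm (corresponding with a treatment OR of 3.71 and a risk difference of 27.5" percentage points). Evaluable size: "35 patients are needed in the systemic thrombolysis and 70 patients in the CDT arm". Recruited: 37 + 74 = 111. Section 10.2 sets the significance level: "A two-sided p-value <0.05 is considered statistically significant".

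**The plan's own figure.** For a pooled z-test with allocation ratio k = 2:

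n₁ = [1.960·√((1 + 1/k)·p̄·q̄) + 0.842·√(p₁q₁ + p₂q₂/k)]² / (p₁ − p₂)²

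With p₁ = 0.46, p₂ = 0.19 and p̄ = (0.46 + 2 × 0.19)/3 = 0.28:

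n₁ = [1.960 × 0.550 + 0.842 × 0.570]² / 0.27² = 33.3, so 34 + 68 = 102, against 35 + 70 = 105 in the protocol.

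Fisher's exact test at 35/70 with a control rate of 0.465 has 80.5% power. For drop-out, 35/0.95 gives 37 and 70/0.95 gives 74. The sample size is therefore reproduced closely. The stated odds ratio of 3.71 and the 27.5-point difference correspond to a control rate of 0.465 (0.46 gives an odds ratio of 3.63).

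**Information available.** Expected primary events are 0.465 × 37 + 0.19 × 74 = 17.2 + 14.1 = 31, before any split into subgroups.

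**Excess of the best-looking subgroup.** Trials of 37 v 74 patients were simulated with the same risks (0.465 v 0.19) for everyone, so that no true subgroup difference exists. In each trial the largest subgroup risk reduction was compared with the overall one. The protocol gives no prevalences; those below are assumptions. Using the primary outcome as the measure of benefit is also an assumption.

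| Candidate factors (assumed prevalence) | Median excess | Excess ≥ 10 points |
|---|---|---|
| Sex (50%) | about 6 points | about 29% of trials |
| Sex (50%), age ≥ 75 (30%), PE subtype (25%) | about 13 points | – |
| The same plus cancer (15%) | about 16 points | about 78% of trials |

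A second set of runs used a control rate of 0.46 and other assumed prevalences (sex, device and PE subtype 50%, age 25%, cancer 15%). With the protocol's three examples (device, sex, cancer) the mean excess was 14 points, and 10 points or more in 53% of trials. With all five factors the figures were 18 points and 77%.

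**If an interaction test at 5% were the gate instead.** For m independent tests, the chance of at least one false positive is 1 − 0.95^m: 14.3% for m = 3, 18.5% for m = 4 and 22.6% for m = 5. The second set of simulations gave 16% for three factors and 26% for five.

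**The case against.** Most of the case against concerns reach and size, and much of it stands.

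- **Near-certainty.** A reader might infer that a spurious subgroup benefit is close to certain. The protocol does not support this. It fixes no threshold, so no single probability follows. Some excess in the largest estimate is almost guaranteed by arithmetic, but an excess of 10 points or more is not. Under a 5% interaction test the chance of a false finding is about 14% to 26%.
- **The gap between a factor's two levels.** In the four-factor simulation the largest such gap has a median of about 32 points, which looks larger than the whole planned effect. That gap is a contrast between two subgroups, not the overstatement in the chosen one. The overstatement is about half as large.
- **Which effect is used.** The protocol does not say that the selected subgroup's own estimate enters the scenario. That is the natural reading, but it is inference, so the bias is conditional on it.
- **Influence on payers.** Nothing in the text says that a subgroup scenario would guide reimbursement more than the two numbered scenarios. The single sentence on sensitivity analysis also does not show what that analysis would leave out.
- **Sparse factors.** Cancer at 15% means about 5 to 6 controls (0.15 × 37) and drives much of the upper end. The adequate-numbers condition, if carried over, would probably exclude it.
- **Detail left to the SAP.** Budget scenario rules may well be set out there. This does not answer the point, because the protocol itself states that subgroups are chosen by observed benefit.

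**Conclusion.** The point holds in a limited form. Section 10.2 states a data-driven selection rule with an open list and no criterion, names a factor absent from its own subgroup list, and attaches the rule to a scenario that is never stated. If the chosen subgroup's own estimate is used, its benefit is overstated by a median of about 6 to 16 points on a true difference of 27.5 points. The range depends on the number and assumed prevalence of the candidate factors, on taking the largest estimate, and on a homogeneous true effect.

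The consequence is confined to a subgroup scenario within one secondary economic objective. The primary analysis, the main cost-effectiveness analysis and the two numbered budget scenarios do not depend on it. This is a minor correction that is worth making.

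**What to change.** Replace the sentence in Protocol section 10.2 with text that does the following:

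1. States the subgroup scenario explicitly as a third scenario, or drops it.
2. Limits it to baseline subgroups fixed before database lock and reconciled with the clinical list in the same section: add cancer to both or remove it. Device type exists only in the CDT arm and so cannot serve as a baseline subgroup; the numerical stratification by device can stay.
3. Deletes selection by observed benefit.
4. Uses the overall randomised effect as the base case, with subgroups changing only eligible numbers, baseline risk and costs.
5. Labels any scenario with a subgroup-specific effect as exploratory and shows its interaction estimate beside it.

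The cost is a few sentences of wording, with no change to sample size, data collection or patient care. The downside is that no confirmatory scenario for an apparent responder group would be available. Making the overall effect the base case is partly a matter of preference, which is why item 5 leaves room for a labelled alternative.
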